## 9.7 Interim Analyses

A preliminary analysis of Part 1 data may be conducted to inform on whether the study will proceed to Part 2.

## 9.8 Multiplicity

No multiplicity adjustment is needed as the study has no hypothesis testing.

## 9.9 Sample Size and Power Calculations

The sample size selected for each population to evaluate the effect of hepatic impairment on the PK of MK-8189 was not chosen to satisfy any a priori statistical requirement. This sample size (N=6-8 per group) has historically been shown to be sufficient for studies of this type and should provide adequate data to support the planned analyses. Nevertheless, estimates of the expected precision of the estimates, based on these sample sizes and the known variability obtained from hepatic PK studies are presented below.

The precision of the estimated ratios of geometric means (hepatic impairment / normal hepatic function) of PK parameters obtained from this study can be assessed by calculating the half-width of the 90% CIs expected for the given sample size and assumed variability. The pooled between-subject standard deviation (on the natural log scale) for AUC0-24 in participants with normal hepatic function and participants with schizophrenia on 4 mg MK-8189 was 0.29  $\ln(nM^{\ast}hr)$  from P003. The pooled between-subject standard deviation for AUC0-24 was obtained using the between subject standard deviation of 0.16  $\ln(nM^{\ast}hr)$  in healthy and between subject deviation of 0.39  $\ln(nM^{\ast}hr)$  in participants with schizophrenia on 4 mg MK-8189 in P003. The variability for AUC0-inf in participants with moderate hepatic impairment is assumed to be similar to the variability in AUC0-24 in participants with schizophrenia for 4 mg dose from P003. The variability for AUC0-inf in participants with normal hepatic function is assumed to be similar to the variability in AUC0-24 in healthy participants for 4 mg dose from P003. Assuming a minimum sample size of 6 participants per population and observed between-subject standard deviation as given above, then the half width of the 90% CIs of GMRs for MK-8189 AUC0-inf on the log scale will be 0.30. The lower and upper 90% confidence limits for the true GMRs will be given by  $OBS/1.35$  and  $OBS*1.35$  for AUC0-inf, where OBS is the observed GMR. Thus, for example, if the observed GMR for AUC0-inf was 1.50, then the 90% CI for the GMR would be 1.11 to 2.03.

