## 9.6 Statistical Methods

### Pharmacokinetics:

At the end of the study, the final analysis will be run on pooled data from both study parts (if both parts are conducted).

Separately for each PK parameter, individual values of AUC0-24, Cmax, C24, AUC0-last, and AUC0-inf will be natural log-transformed and evaluated with a linear fixed effects model containing a fixed effect for population (each hepatic impairment group, and normal hepatic function). An unstructured covariance matrix will be used to allow for unequal population variances via the REPEATED and GROUP statement in SAS PROC MIXED. Kenward and Roger's method will be used to calculate the denominator degrees of freedom for the fixed effect (DDFM=KR). Ninety-five percent (95%) CIs for the least squares means for each population will be constructed on the natural log scale and will reference the t-distribution. Exponentiating the least-squares means and their corresponding 95% CIs will yield estimates for the population geometric means and confidence intervals about the geometric means on the original scale. Sample SAS code is given below:

```
proc mixed data=data;
  class population;
  model lnpk = population /ddf=kr;
  repeated/ group= population;
  lsmeans population /cl alpha=0.05;
run;
```

To compare participants in each hepatic impairment population to participants with normal hepatic function, a two sided 90% confidence interval for the true difference in means (hepatic impairment – normal hepatic function) will be calculated for AUC0-24, Cmax, AUC0-last, and AUC0-inf using the mean square error from the model and referencing a t-distribution. These confidence limits will be exponentiated to obtain the 90% confidence interval for the true ratio of geometric means (hepatic impairment/normal hepatic function) for each PK parameter and each hepatic population.

Figures showing individual PK values with GMs (95% CIs) by population, plotted on the natural log scale, will be provided for PK parameters AUC0-24, Cmax, AUC0-last, and AUC0-inf. A figure showing the GMR (hepatic impairment/normal hepatic function) and corresponding 90% CI will be provided for PK parameters AUC0-24, Cmax, AUC0-last, and AUC0-inf.

The above analyses will be carried out for PK calculated from both total and unbound concentrations.

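### The 90% CI half-width of 0.30 in Section 9.9 comes from a pooled-variance interval; the unequal-variance model planned in Section 9.6 gives 0.33 with the plan's own SDs

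*Combined protocol and SAP*

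**What the plan says.** **Section 9.9 (precision).** The calculation starts from study P003 at 4 mg. The pooled between-subject SD of ln AUC0-24 "in participants with normal hepatic function and participants with schizophrenia on 4 mg MK-8189 was 0.29". Its two components are given as 0.16 "in healthy and between subject deviation of 0.39" in participants with schizophrenia. The section then carries these over by group: AUC0-inf variability in moderate impairment is taken to resemble the schizophrenia value, and in normal hepatic function the healthy value. The result is introduced with "Assuming a minimum sample size of 6 participants per population and observed between-subject standard deviation as given above", and the conclusion is that "the half width of the 90% CIs of GMRs for MK-8189 AUC0-inf on the log scale will be 0.30". The limits follow as a factor of 1.35 either way, with 1.11 to 2.03 as the example at an observed GMR of 1.50.

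**Section 9.6 (analysis).** "An unstructured covariance matrix will be used to allow for unequal population variances via the REPEATED and GROUP statement in SAS PROC MIXED". Degrees of freedom are by Kenward and Roger's method, and the sample code has a REPEATED statement with GROUP=population. For the comparison, "a two sided 90% confidence interval for the true difference in means (hepatic impairment – normal hepatic function) will be calculated". The same sentence says that this interval uses the model's mean square error.

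**The concern.** Section 9.9 names two SDs whose variances differ almost sixfold (0.1521 / 0.0256 = 5.9), and Section 9.6 chooses a model that allows for such a difference. The printed half-width nevertheless uses a single SD of 0.29 and the degrees of freedom of an equal-variance comparison. The precision paragraph therefore describes a different analysis from the one planned.

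This is an estimation study, so the width of the interval is its main statistical performance measure, and AUC0-inf is a primary endpoint. Section 9.9 states precision for no other endpoint. If the figure is too narrow, readers will expect tighter estimates than the planned model would give under the plan's own assumptions.

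**Working it through.** **Inputs**

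- Two-sided 90% interval, so the t quantile at 0.95 (Section 9.6).
- n = 6 per group (Section 9.9).
- ln-scale SDs of 0.16 for normal function and 0.39 for moderate impairment; pooled SD of 0.29 (Section 9.9).
- One variance per population and Kenward-Roger degrees of freedom (Section 9.6). For a contrast of two group means these equal the Welch-Satterthwaite degrees of freedom.

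**1. The plan's own figure**

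Half-width = t(0.95, 10) × SD × √(2/n) = 1.812 × 0.29 × √(2/6) = 0.303. The factor is exp(0.3035) = 1.354, and the limits at a GMR of 1.50 are 1.107 to 2.032. This reproduces 0.30, 1.35 and 1.11 to 2.03.

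**2. The planned model with the plan's SDs**

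- Squared standard errors: 0.16²/6 = 0.004267 and 0.39²/6 = 0.025350.
- SE = √(0.004267 + 0.025350) = 0.1721.
- df = (0.004267 + 0.025350)² / (0.004267²/5 + 0.025350²/5) = 6.64.
- t(0.95, 6.64) = 1.910.
- Half-width = 1.910 × 0.1721 = 0.329.
- Factor = exp(0.3288) = 1.389; limits at 1.50: 1.50/1.389 = 1.08 and 1.50 × 1.389 = 2.08.

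Relative to this, the pooled calculation is 1 − 0.3035/0.3288 = 7.7% too narrow on the log scale.

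**3. Could rounding of the SDs explain it?**

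With SDs anywhere in 0.155–0.165 and 0.385–0.395, step 2 gives 0.324 to 0.333. It does not reach 0.30.

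**4. SDs taken as true rather than observed values**

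Sample variances were simulated as scaled chi-square with 5 df per group. Under the unequal-variance model (400,000 draws) the mean half-width is 0.318 and the median 0.310, and 46% of trials have 0.30 or less. Under an equal-variance interval with the same SDs the mean is 0.301.

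**5. Summary**

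| Calculation | Half-width | Factor | Limits at GMR 1.50 |
|---|---|---|---|
| Equal variance, SD 0.29, 10 df (reproduces Section 9.9) | 0.303 | 1.35 | 1.11 to 2.03 |
| Equal variance, SD √((0.0256 + 0.1521)/2) = 0.298, 10 df | 0.312 | 1.37 | 1.10 to 2.05 |
| Planned model, n = 6 per group | 0.329 | 1.39 | 1.08 to 2.08 |
| Planned model, n = 8 per group (df 9.29, SE 0.1490) | 0.272 | 1.31 | 1.14 to 1.97 |

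**The case against.** The strongest objection concerns which model governs. Section 9.6 says the interval for the difference uses the model's mean square error, which is the language of a pooled error term, and the sample code has no statement for the difference. This stands as an ambiguity to be resolved. It does not rescue the figure as written: a model with one variance per group has no single mean square error, and the text, the GROUP option and the Kenward-Roger method all point to separate variances.

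A second objection is that Section 9.9 introduces its figure as the width to be expected. On that reading the planned model averages 0.318, not 0.329. This is fair as to size, but 0.318 is still not 0.30, and the later reference to observed SDs favours entering them directly.

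A reader might also infer more than the documents support:

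- *That 0.30 is an arithmetic slip.* It is not; step 1 reproduces it. The fault is a mismatch between Sections 9.6 and 9.9.
- *That the design misses 0.30 under any variance method.* It does not. With 0.16 and 0.39 as true SDs, the mean equal-variance half-width is 0.301. An equal-variance model with three groups of six (15 df, SD 0.298) gives 0.302.
- *That 0.29 is itself wrong.* Equal-weight pooling gives 0.298, but 0.29 is presented as a P003 result. Unequal group sizes in P003, which the documents do not give, could explain it. Rounding alone can just do so, since √((0.155² + 0.385²)/2) = 0.2935.
- *That the sample size or the Part 2 decision depends on this figure.* Section 9.9 says N was not set by a statistical requirement, Section 9.8 says there is no hypothesis testing, and Sections 4.1 and 4.2 tie Part 2 to a clinically meaningful rise in exposure.

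**Conclusion.** The precision stated for AUC0-inf does not match the planned analysis. Under the group-specific-variance model, with 0.16 and 0.39 entered as observed SDs and six per group, the half-width is 0.33 rather than 0.30 and the factor 1.39 rather than 1.35. With the SDs taken as true values the mean half-width is about 0.32. On neither reading does the planned model give 0.30 as its observed-SD or mean half-width.

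The practical effect is modest. In the plan's example the lower limit moves from 1.11 to 1.08 and the upper from 2.03 to 2.08, and both intervals exclude 1. The interval finally reported will come from the trial data and the model in Section 9.6, so it is unaffected.

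The conclusion rests on the GROUP specification governing the comparison, and on the plan's assumption that P003 AUC0-24 variability carries over to AUC0-inf. It applies to moderate impairment against normal function; Section 9.9 assigns no separate SD to mild impairment.

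**What to change.** In Section 9.9, restate the figures for n = 6 per group as a half-width of 0.33, a factor of 1.39 and limits of 1.08 to 2.08 at an observed GMR of 1.50. Optionally add 0.27, 1.31 and 1.14 to 1.97 for n = 8 per group. Say that they come from the unequal-variance model with SDs of 0.16 and 0.39 entered as observed values. The pooled 0.29 may stay as a P003 result but should not be the basis of the precision figures.

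In Section 9.6, replace the reference to the mean square error with the standard error of the contrast and its Kenward-Roger degrees of freedom from the GROUP=population model.

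The cost is one paragraph in Section 9.9 and one phrase in Section 9.6. No participants are added, and the only downside is a slightly less favourable stated precision.

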## 10 SUPPORTING DOCUMENTATION AND OPERATIONAL CONSIDERATIONS

### 10.1 Appendix 1: Regulatory, Ethical, and Study Oversight Considerations

#### 10.1.1 Code of Conduct for Clinical Trials

Merck Sharp and Dohme Corp., a subsidiary of Merck & Co., Inc. (MSD)

#### Code of Conduct for Interventional Clinical Trials

##### I. Introduction

###### A. Purpose

MSD, through its subsidiaries, conducts clinical trials worldwide to evaluate the safety and effectiveness of our products. As such, we are committed to designing, implementing, conducting, analyzing, and reporting these trials in compliance with the highest ethical and scientific standards. Protection of participants in clinical trials is the overriding concern in the design and conduct of clinical trials. In all cases, MSD clinical trials will be conducted in compliance with local and/or national regulations (including all applicable data protection laws and regulations), and International Council for Harmonisation Good Clinical Practice (ICH-GCP), and also in accordance with the ethical principles that have their origin in the Declaration of Helsinki.

###### B. Scope

Highest ethical and scientific standards shall be endorsed for all clinical interventional investigations sponsored by MSD irrespective of the party (parties) employed for their execution (e.g., contract research organizations, collaborative research efforts). This Code is not intended to apply to trials that are observational in nature, or which are retrospective. Further, this Code does not apply to investigator-initiated trials, which are not under the full control of MSD.

##### II. Scientific Issues

###### A. Trial Conduct

###### 1. Trial Design

Except for pilot or estimation trials, clinical trial protocols will be hypothesis-driven to assess safety, efficacy and/or pharmacokinetic or pharmacodynamic indices of MSD or comparator products. Alternatively, MSD may conduct outcomes research trials, trials to assess or validate various endpoint measures, or trials to determine patient preferences, etc.

The design (i.e., participant population, duration, statistical power) must be adequate to address the specific purpose of the trial and shall respect the data protection rights of all participants, trial site staff and, where applicable, third parties. Participants must meet protocol entry criteria to be enrolled in the trial.

###### 2. Site Selection

MSD selects investigative sites based on medical expertise, access to appropriate participants, adequacy of facilities and staff, previous performance in clinical trials, as well as budgetary considerations. Prior to trial initiation, sites are evaluated by MSD personnel (or individuals acting on behalf of MSD) to assess the ability to successfully conduct the trial.

###### 3. Site Monitoring/Scientific Integrity

Investigative trial sites are monitored to assess compliance with the trial protocol and Good Clinical Practice (GCP). MSD reviews clinical data for accuracy, completeness, and consistency. Data are verified versus

source documentation according to standard operating procedures. Per MSD policies and procedures, if potential fraud, scientific/research misconduct, privacy incidents/breaches or Clinical Trial-related Significant Quality Issues are reported, such matters are investigated. When necessary, appropriate corrective and/or preventative actions are defined and regulatory authorities and/or ethics review committees are notified.

#### **B. Publication and Authorship**

Regardless of trial outcome, MSD commits to publish the primary and secondary results of its registered trials of marketed products in which treatment is assigned, according to the pre-specified plans for data analysis. To the extent scientifically appropriate, MSD seeks to publish the results of other analyses it conducts that are important to patients, physicians, and payers. Some early phase or pilot trials are intended to be hypothesis-generating rather than hypothesis testing; in such cases, publication of results may not be appropriate since the trial may be underpowered and the analyses complicated by statistical issues such as multiplicity.

MSD's policy on authorship is consistent with the recommendations published by the International Committee of Medical Journal Editors (ICMJE). In summary, authorship should reflect significant contribution to the design and conduct of the trial, performance or interpretation of the analysis, and/or writing of the manuscript. All named authors must be able to defend the trial results and conclusions. MSD funding of a trial will be acknowledged in publications.

### **III. Participant Protection**

#### **A. Regulatory Authority and Ethics Committee Review (Institutional Review Board [IRB]/Independent Ethics Committee [IEC])**

All protocols and protocol amendments will be submitted by MSD for regulatory authority acceptance/authorization prior to implementation of the trial or amendment, in compliance with local and/or national regulations.

The protocol, protocol amendment(s), informed consent form, investigator's brochure, and other relevant trial documents must be reviewed and approved by an IRB/IEC before being implemented at each site, in compliance with local and/or national regulations. Changes to the protocol that are required urgently to eliminate an immediate hazard and to protect participant safety may be enacted in anticipation of ethics committee approval. MSD will inform regulatory authorities of such new measures to protect participant safety, in compliance with local and/or national regulations.

#### **B. Safety**

The guiding principle in decision-making in clinical trials is that participant welfare is of primary importance. Potential participants will be informed of the risks and benefits of, as well as alternatives to, trial participation. At a minimum, trial designs will take into account the local standard of care.

All participation in MSD clinical trials is voluntary. Participants enter the trial only after informed consent is obtained. Participants may withdraw from an MSD trial at any time, without any influence on their access to, or receipt of, medical care that may otherwise be available to them.

#### **C. Confidentiality**

MSD is committed to safeguarding participant confidentiality, to the greatest extent possible, as well as all applicable data protection rights. Unless required by law, only the investigator, Sponsor (or individuals acting on behalf of MSD), ethics committee, and/or regulatory authorities will have access to confidential medical records that might identify the participant by name.

#### **D. Genomic Research**

Genomic research will only be conducted in accordance with a protocol and informed consent authorized by an ethics committee.

#### **IV. Financial Considerations**

##### **A. Payments to Investigators**

Clinical trials are time- and labor-intensive. It is MSD's policy to compensate investigators (or the sponsoring institution) in a fair manner for the work performed in support of MSD trials. MSD does not pay incentives to enroll participants in its trials. However, when enrollment is particularly challenging, additional payments may be made to compensate for the time spent in extra recruiting efforts.

MSD does not pay for participant referrals. However, MSD may compensate referring physicians for time spent on chart review and medical evaluation to identify potentially eligible participants.

##### **B. Clinical Research Funding**

Informed consent forms will disclose that the trial is sponsored by MSD, and that the investigator or sponsoring institution is being paid or provided a grant for performing the trial. However, the local ethics committee may wish to alter the wording of the disclosure statement to be consistent with financial practices at that institution. As noted above, all publications resulting from MSD trials will indicate MSD as a source of funding.

##### **C. Funding for Travel and Other Requests**

Funding of travel by investigators and support staff (e.g., to scientific meetings, investigator meetings, etc.) will be consistent with local guidelines and practices.

#### **V. Investigator Commitment**

Investigators will be expected to review MSD's Code of Conduct as an appendix to the trial protocol, and in signing the protocol, agree to support these ethical and scientific standards.

##### **10.1.2 Financial Disclosure**

Financial Disclosure requirements are outlined in the US Food and Drug Administration Regulations, Financial Disclosure by Clinical Investigators (21 CFR Part 54). It is the Sponsor's responsibility to determine, based on these regulations, whether a request for Financial Disclosure information is required. It is the investigator's/subinvestigator's responsibility to comply with any such request.

The investigator/subinvestigator(s) agree, if requested by the Sponsor in accordance with 21 CFR Part 54, to provide his/her financial interests in and/or arrangements with the Sponsor to allow for the submission of complete and accurate certification and disclosure statements. The investigator/subinvestigator(s) further agree to provide this information on a Certification/Disclosure Form, commonly known as a financial disclosure form, provided by the Sponsor. The investigator/subinvestigator(s) also consent to the transmission of this information to the Sponsor in the United States for these purposes. This may involve the transmission of information to countries that do not have laws protecting personal data.

##### **10.1.3 Data Protection**

The Sponsor will conduct this study in compliance with all applicable data protection regulations.

Participants will be assigned a unique identifier by the Sponsor. Any participant records or datasets that are transferred to the Sponsor will contain the identifier only; participant names or any information that would make the participant identifiable will not be transferred.

The participant must be informed that his/her personal study-related data will be used by the Sponsor in accordance with local data protection law. The level of disclosure must also be explained to the participant.

The participant must be informed that his/her medical records may be examined by Clinical Quality Assurance auditors or other authorized personnel appointed by the Sponsor, by appropriate IRB/IEC members, and by inspectors from regulatory authorities.

#### **10.1.3.1 Confidentiality of Data**

By signing this protocol, the investigator affirms to the Sponsor that information furnished to the investigator by the Sponsor will be maintained in confidence, and such information will be divulged to the IRB, IEC, or similar or expert committee; affiliated institution and employees, only under an appropriate understanding of confidentiality with such board or committee, affiliated institution and employees. Data generated by this study will be considered confidential by the investigator, except to the extent that it is included in a publication as provided in the Publications section of this protocol.

#### **10.1.3.2 Confidentiality of Participant Records**

By signing this protocol, the investigator agrees that the Sponsor (or Sponsor representative), IRB/IEC, or regulatory authority representatives may consult and/or copy study documents to verify worksheet/CRF data. By signing the consent form, the participant agrees to this process. If study documents will be photocopied during the process of verifying worksheet/CRF information, the participant will be identified by unique code only; full names/initials will be masked prior to transmission to the Sponsor.

By signing this protocol, the investigator agrees to treat all participant data used and disclosed in connection with this study in accordance with all applicable privacy laws, rules and regulations.

